# PROTOCOL SYNOPSIS

Gilead Sciences, Inc. [name]

	 	
Study Title:	A Phase 2a, Open-Label Study to Evaluate the Safety and Efficacy of Selgantolimod (SLGN)-Containing Combination Therapies for the Treatment of Chronic Hepatitis B (CHB)	
IND Number:	This is a non-IND study	
ANZCTR Trial ID:	Not Available	
Clinical Trials.gov Identifier:	NCT04891770	
EudraCT Number:	2021-000672-11	
Study Centers Planned:	Approximately 30 centers globally	
Objectives:	The primary objectives of this study are as follows:	
	To evaluate the safety and tolerability of study treatment(s)	
	To evaluate the efficacy of study treatment(s) as measured by the proportion of participants who achieve functional cure, defined as negative qualitative hepatitis B surface antigen (HBsAg loss) and hepatitis B virus (HBV) DNA < lower limit of quantitation (LLOQ) at Follow-up (FU) Week 24  The secondary objectives of this study are as follows:	
	To evaluate the proportion of participants with HBsAg loss with and without anti-HBsAg seroconversion during the study	
	To evaluate in participants with CHB who are hepatitis B e antigen (HBeAg) positive at baseline the proportion of participants who achieve HBeAg loss with and without anti-HBeAg seroconversion during the study	
	To evaluate the proportion of participants who remain off nucleos(t)ide(s) (NUC) treatment during FU	
	To evaluate the proportion of participants experiencing HBV virologic breakthrough (defined as confirmed HBV DNA ≥ LLOQ after 2 consecutive HBV DNA < LLOQ in participants who are complying with NUC therapy OR confirmed HBV DNA ≥ 1 log 10 IU/mL increase from nadir on treatment) during study treatment(s)  CCI	

### **Study Design:**

This is a Phase 2, open-label study to evaluate the safety and efficacy of SLGN-containing combination therapies in CHB participants. The study will consist of 2 cohorts (Cohorts 1, and 2).

Approximately 40 NUC-suppressed and 60 viremic CHB-infected participants, may be enrolled and assigned into a cohort below. Each cohort will enroll a minimum of 20% HBeAg-positive participants, and up to 20% of participants can have HBsAg < 100 IU/mL.

## **NUC-suppressed Cohort**

# Cohort 1 (n = 40):

- Tenofovir alafenamide (TAF) 25-mg tablet administered orally once daily for 36 weeks
- VIR-2218 200 mg administered as subcutaneous (SC) injection once every 4 weeks for 24 weeks (total 6 doses)

At Week 12, add-on and initiate the below treatment:

- SLGN 3 mg (2 × 1.5-mg tablets) administered orally while fasting once a week on the same day for 24 weeks (total 24 doses)
- Nivolumab 0.3 mg/kg administered intravenously (IV) once every 4 weeks for up to 24 weeks (up to 6 doses)

### **Viremic Cohort (Cohort 2)**

### Cohort 2 (n = 60):

Participants will be randomized 2:1 into Cohort 2 Groups A and B and stratified by HBsAg > or  $\le 3 \log_{10} IU/mL$ .

# Group A (n = 40):

• VIR-2218 200 mg administered as SC injection once every 4 weeks for 24 weeks (total 6 doses)

At Week 12, add-on and initiate the below treatment:

- SLGN 3 mg (2 × 1.5-mg tablets) administered orally while fasting once a week on the same day for 24 weeks (total 24 doses)
- Nivolumab 0.3 mg/kg administered IV once every 4 weeks for up to 24 weeks (up to 6 doses)

### Group B (n = 20):

- SLGN 3 mg (2 × 1.5-mg tablets) administered orally while fasting once a week on the same day for up to 24 weeks (up to 24 doses)
- Nivolumab 0.3 mg/kg administered IV once every 4 weeks for up to 24 weeks (up to 6 doses)

NOTE: Nivolumab dosing was stopped in this study. This was a sponsor decision based on a benefit risk assessment of the use of nivolumab in HBV cure

As the study had completed enrollment and all participants were in treatment when the decision was made to stop nivolumab administration, the following amendments to the protocol were implemented:

- Stop further nivolumab administration for all study participants across all cohorts
- Continue treatment with VIR-2218 and SLGN through Week 36 for Cohorts 1 and 2 (Group A)
- Discontinue all study treatment for Cohort 2 Group B
  participants with next follow up visit being EOT for those still
  in treatment period
- Stop all sample collections related to nivolumab
- NUC therapy cessation is no longer required for our NUC treated patients (Cohort 1)

# Follow-up Period:

At the end of treatment, all participants will enter a FU period

- All participants not on TAF treatment at end of treatment (EOT)
   will enter a treatment-free follow-up (TFFU) period
- Participants who are on TAF treatment will continue TAF treatment over the duration of the follow up period

[figure not shown]
Participants who initiated TFFU prior to the approval of this amendment and stopped NUC treatment may continue off NUCs after discussion between participant and investigator on the benefits and risks of continuing off NUCs in TFFU. Those who decide to restart NUCs would initiate commercial NUC treatment.

#### Pharmacokinetic assessments

### Sparse Pharmacokinetic Collection

Sparse (timed) plasma/serum PK samples will be obtained at specific in-clinic treatment visits at any time between 1 to 5 hours postdose relative to SLGN and/or VIR-2218 administration unless otherwise indicated.

All elevated serum ALT should be confirmed as soon as possible and ideally within 3 days of receipt of results. During the visit, a clinical assessment of the participant should be performed. The assessment should include a physical examination, evaluation of the participant's mental status, and the following laboratory tests:

- Laboratory parameters: serum ALT and aspartate aminotransferase (AST), total bilirubin, gamma-glutamyl transferase (GGT), international normalized ratio (INR), serum albumin, and alcohol screening.
- If the ALT elevation is confirmed, the central clinical laboratory will conduct reflex testing for plasma HBV DNA, serology for HBV (HBsAg, HBsAb, HBeAg, and HBeAb), hepatitis D virus (HDV), hepatitis A virus (HAV) immunoglobulin M (IgM), hepatitis C virus (HCV), and hepatitis E virus (HEV).
- Liver biopsy may be collected for participants meeting Hy's law (ALT > 3 × ULN and Total Bilirubin > 2 × ULN; AST > 3 × ULN and Total Bilirubin > 2 × ULN) with suspected drug-induced-liver-injury (DILI)

Based on the results of the confirmatory tests, the following study treatment modifications are recommended (Table 1):

Table 1. Dose Modification and Monitoring

Liver Toxicity Parameters	Action
Confirmed, ALT $\geq$ 10 × ULN without evidence of hepatic toxicity as defined below	Cohort 1: Hold VIR-2218 and SLGN treatment. Participant should be monitored weekly or more frequently if clinically indicated until ALT < 5 × ULN. Restarting study treatment (VIR-2218, SLGN) may be considered when ALT < 5 × ULN in discussion with the medical monitor. Study treatment should be restarted in line with the original assigned administration schedule.
	Cohort 2: Initiate TAF 25 mg once daily and hold SLGN, and/or VIR-2218 dose. Participant should be monitored weekly or more frequently if clinically indicated until ALT < 5 × ULN.  Restarting study treatment (VIR-2218, and SLGN) may be considered when ALT < 5 × ULN in discussion with the medical monitor. Study treatment should be restarted in line with the original assigned administration schedule.
Persistent ALT > 2 × baseline and ≥ 5 × ULN without evidence of hepatic toxicity, as defined below	Continue study treatment(s), ALT should be evaluated every 2 weeks or more frequently as clinically needed, until ALT < 5 × ULN

Confirmed ALT $> 2 \times$ nadir, with
evidence of hepatic toxicity,
defined as any one of the
following confirmed laboratory
abnormalities:

- Total bilirubin  $> 2 \times ULN$
- Elevated INR > 0.5 above baseline AND > ULN
- Abnormal serum albumin
   1 g/dL decrease from baseline

**Cohort 1:** Permanently discontinue study treatment(s) except TAF 25 mg once daily. Participant should be monitored weekly until ALT < 5 × ULN, and total bilirubin, INR, and albumin values return to normal or baseline levels

**Cohort 2:** Initiate commercially approved NUC treatment once daily and permanently discontinue study treatment(s). Participant should be monitored weekly until ALT  $< 5 \times ULN$ , and total bilirubin, albumin, and/or INR values return to normal or baseline levels

ALT = alanine aminotransferase; INR = international normalized ratio; NUC = nucleos(t)ide(s); SLGN = selgantolimod; TAF = tenofovir alafenamide; ULN = upper limit of normal

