## 7.7.5. ALT Elevation or Flare Management on Treatment and Treatment-Free Follow-up

## **On-Treatment ALT Management**

Participants with on-treatment serum ALT elevation  $> 2 \times$  nadir or  $> 2 \times$  baseline value and  $\ge 5 \times$  ULN, with or without associated symptoms should be managed according to the guidance below.

All elevated serum ALT should be confirmed as soon as possible and ideally within 3 days of receipt of results. During the visit, a clinical assessment of the participant should be performed. The assessment should include a physical examination, evaluation of the participant's mental status, and the following laboratory tests:

- Laboratory parameters: serum ALT and AST, total bilirubin, GGT, INR, and serum albumin, alcohol screening
- If the ALT elevation is confirmed, the central clinical laboratory will conduct reflex testing for plasma HBV DNA, serology for HBV (HBsAg, HBsAb, HBeAg and HBeAb), HDV, hepatitis A virus (HAV) IgM, HCV, and HEV
- Liver biopsy may be collected for participants meeting Hy's law (ALT >  $3 \times ULN$  and Total Bilirubin >  $2 \times ULN$ ; AST >  $3 \times ULN$  and Total Bilirubin >  $2 \times ULN$ ) with suspected DILI

Additional confirmatory tests such as HDV RNA, HDV IgM, and HEV RNA may be performed locally as per local regulations after further discussion with the Gilead's Medical Monitor.

Based on the results of the confirmatory tests, the following study treatment modifications are recommended (Table 6).

Table 6. Dose Modification and Monitoring

Liver Toxicity Parameters	Action
Confirmed, ALT $\geq 10 \times ULN$ without evidence of hepatic toxicity as defined below	Cohort 1: Hold VIR-2218 and SLGN treatment. Participant should be monitored weekly or more frequently if clinically indicated until ALT < 5 × ULN. Restarting VIR-2218 and/or SLGN treatment may be considered when ALT < 5 × ULN in discussion with the medical monitor. Study treatment should be restarted in line with the original assigned administration schedule.  Cohort 2: Initiate TAF 25 mg once daily and hold VIR-2218 and SLGN dose. Participant should be monitored weekly or more frequently if clinically indicated until ALT < 5 × ULN. Restarting VIR-2218 and/or SLGN treatment may be considered when ALT < 5 × ULN in discussion with the medical monitor. Study treatment should be restarted in line with the original assigned administration schedule.

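### For confirmed ALT ≥ 10 × ULN in Cohort 2, synopsis Table 1 lets a site hold either or both study drugs, while Table 6 in Section 7.7.5 holds both

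*Supplement*

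**What the plan says.** Two tables headed Dose Modification and Monitoring govern ALT elevations on treatment: Table 1 in the Protocol Synopsis and Table 6 in Section 7.7.5. Their first rows share one trigger, confirmed ALT at or above "10 × ULN without evidence of hepatic toxicity as defined below".

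For Cohort 2 the hold instruction reads:
- Synopsis Table 1: "Initiate TAF 25 mg once daily and hold SLGN, and/or VIR-2218 dose".
- Section 7.7.5, Table 6: "Initiate TAF 25 mg once daily and hold VIR-2218 and SLGN dose".

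The Cohort 2 restart sentence reads:
- Synopsis Table 1: "Restarting study treatment (VIR-2218, and SLGN) may be considered when ALT < 5 × ULN in discussion with the medical monitor".
- Section 7.7.5, Table 6: "Restarting VIR-2218 and/or SLGN treatment may be considered when ALT < 5 × ULN in discussion with the medical monitor".

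For Cohort 1 both tables give the same hold instruction, "Hold VIR-2218 and SLGN treatment".

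Both tables are introduced as advice; in Section 7.7.5 the lead-in is "the following study treatment modifications are recommended (Table 6"). Section 6.9.2 refers the reader to Section 7.7 for ALT-related dose modification by treatment and cohort.

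**The concern.** The first row covers the highest ALT level that either table names, and it tells the site what to do with study drug. In Table 1 the *and/or* is attached to the hold, so a site using the synopsis could stop one drug and keep giving the other. A site using Section 7.7.5 would stop both. Each would be following the protocol.

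The conflict lies in the cohort with less room below the trigger. Exclusion criterion 2d admits Cohort 2 participants with ALT up to just under 5 × ULN, against just under 2 × ULN in Cohort 1. A participant at the upper entry limit reaches 10 × ULN with a 2-fold rise in Cohort 2 (10 / 5) and a 5-fold rise in Cohort 1 (10 / 2).

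What is at stake is consistent safety handling and, secondarily, a clear description of what was given. Section 8.6.1 summarises exposure by treatment cohort, and Section 8.5.1 estimates functional cure per cohort. If drug-specific exposure after a flare depends on which table the site used, those summaries mix two handling rules without showing it.

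**Working it through.** No planned figure is involved, so the check is a comparison of text followed by a count of where the difference can bite.

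**Step 1: compare the two Cohort 2 cells.**

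| Element | Synopsis Table 1 | Section 7.7.5, Table 6 |
|---|---|---|
| Trigger | confirmed ALT ≥ 10 × ULN, no hepatic toxicity | same |
| TAF 25 mg daily | start | start |
| Hold | SLGN *and/or* VIR-2218 | VIR-2218 *and* SLGN |
| Monitoring | weekly or more often until ALT < 5 × ULN | same |
| Restart threshold | ALT < 5 × ULN, discussed with medical monitor | same |
| Drugs named at restart | VIR-2218 *and* SLGN | VIR-2218 *and/or* SLGN |

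Taken literally, Table 1 permits three actions (hold SLGN alone, hold VIR-2218 alone, hold both). Table 6 permits one.

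**Step 2: who in Cohort 2 is still dosed.** The current text says "Discontinue all study treatment for Cohort 2 Group B" (Synopsis; also Section 3.2.1). On-treatment Cohort 2 is therefore Group A, planned n = 40.

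**Step 3: when Group A is on both drugs (Section 6.5).**
- VIR-2218: Day 1 and Weeks 4, 8, 12, 16 and 20, which is 6 doses.
- SLGN: weekly from Week 12 through Week 35, which is 35 − 12 + 1 = 24 doses.
- Visits at which both are due: Weeks 12, 16 and 20. Counting the last 4-week VIR-2218 interval, the overlap ends at Week 20 + 4 = Week 24.

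Before Week 12 only VIR-2218 is given. After the Week 20 dose only SLGN is given. In those periods holding the drug in use satisfies both tables on a sensible reading, so the conflict has practical content only from about Week 12 to Week 20, or 24.

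**Step 4: how much dosing could differ.** If a site continues VIR-2218 where Table 6 would hold it, at most 3 of the 6 doses are in question (Weeks 12, 16 and 20). If it continues SLGN instead, one dose is in question for each week that the hold would have lasted; the documents give no expected duration. Holding one drug already counts as an interruption, so the Section 8.6.2 summary of events leading to temporary interruption of any study drug should change little. The difference falls mainly on drug-specific exposure.

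**Step 5: does another passage settle it?** Section 6.9.2 points to Section 7.7, where Table 6 sits, but states no precedence over the synopsis. The general hold rule for laboratory abnormalities in Section 6.9.1 excepts ALT. I found no statement of which table governs.

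**The case against.** The best counter-reading is that *and/or* simply means whichever drug the participant is receiving. Group A is on one drug for much of its schedule, and on that reading the two tables agree. The phrase and its stray comma may also be left over from the nivolumab wording or from Group B, which never received VIR-2218. Section 6.9.2 directs readers to the body of the protocol, Section 7.7 sends questions to the medical monitor, and both tables are framed as recommendations.

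Much of this stands as mitigation. It does not remove the conflict. Cohort 1 follows the same staged schedule for these two drugs, yet both tables tell it to hold VIR-2218 *and* SLGN, so staging does not explain wording found only for Cohort 2. A leftover phrase is a plausible origin, but a site must act on the text as printed, and the hold sentence does not call for discussion with the medical monitor.

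A reader might go further in three ways that the documents do not support:
- That the same flare *is* dosed differently. The text shows only that it *can* be; actual site practice is not documented.
- That, with Group B stopped, *and/or* can only be read as a choice. Group A is itself on one drug outside the overlap window.
- That Cohort 1 is equally exposed through the restart wording. Its hold instruction is the same in both tables. In both, restart is something that may be considered with the medical monitor, and the synopsis parenthesis names the study treatments without requiring them to resume together.

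**Conclusion.** The point holds in limited form, as an internal inconsistency of low severity. For confirmed ALT ≥ 10 × ULN without hepatic toxicity in Cohort 2, the literal wording of synopsis Table 1 allows continued dosing of a study drug that Table 6 withholds. The restart difference is a lesser matter of wording.

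It applies to Group A participants who meet the trigger at about Weeks 12 to 20, or to Week 24 on the wider count. The planned 40 is a ceiling, not an estimate: no flare frequency is given, and all participants were already enrolled and in treatment when nivolumab was stopped, so some may have passed the window before this text applied. Any effect on the FU Week 24 result is unquantified; that analysis is a per-cohort proportion with an exact interval, by assigned treatment.

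The conclusion assumes that a site could reasonably consult either table, since neither is said to override the other.

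**What to change.** Reconcile synopsis Table 1 with Table 6 in Section 7.7.5 so that the first row carries identical hold and restart wording. If the intended meaning is to hold whichever drugs are being given, say so in both places. Aligning the restart sentence for Cohort 1 in the same edit removes the lesser mismatch. Which wording stands is the sponsor's clinical decision, and this review takes no position on it.

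The cost is a text change, at most in the two tables. No visit, assessment, data field or analysis changes. If the study has moved past the point where an amendment is useful, a short clarification to sites would serve, and the study report could list, for any Group A participant who met this trigger in the overlap window, which drugs were held.

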# **Treatment-Free Follow-up ALT Management**

All eligible participants will enter a TFFU period after completion of study treatment, in which they will undergo close safety monitoring. The proportion of participants who achieve HBsAg loss or are able to remain off NUC therapy during TFFU period will be assessed. Table 2 provides guidance for initiating commercially approved NUC treatment, in participants who experience rebound of HBV DNA and ALT levels. Any deviation from Table 2 should be discussed in advance with the medical monitor.

If unscheduled visits are required for ALT monitoring, a clinical assessment of the participant should be performed. The assessment should include a physical examination, evaluation of the participant's mental status and the following laboratory tests:

- Laboratory parameters: serum ALT and AST, total and direct bilirubin, GGT, INR, serum albumin, plasma HBV DNA, quantitative HBsAg, peripheral blood mononuclear cells (PBMC) for immune profiling, and alcohol screen.
- At the initial confirmatory visit, collect serology for HDV, HAV IgM, HCV, and HEV.

Participants with HBV DNA < LLOQ and ALT elevation/flare meeting any of the below table criteria, should be evaluated for alternative liver disease etiologies by the investigator and in discussion with the medical monitor. Liver biopsy may be collected at the investigator's discretion.

Participants with HBV DNA > LLOQ and ALT elevation/flare should be managed according to the following table:

Table 2. Starting Commercial NUC Treatment Criteria

Liver Toxicity Parameters	Action
---------------------------	--------

Confirmed ALT $\geq$ 10 × ULN with no evidence of hepatic toxicity, as defined below.	Initiate NUC treatment and monitor weekly until ALT < 5 × ULN, and every 2 weeks until ALT < 2 × ULN, or more frequently if clinically indicated.
ALT $\geq$ 5 × ULN without evidence of hepatic toxicity, as defined below	ALT should be evaluated every 2 weeks or more frequently as clinically needed, until ALT < 2 × ULN.
Confirmed ALT > ULN with evidence of hepatic toxicity, defined as any one of the following confirmed laboratory abnormalities:  • Total bilirubin > 2 × nadir AND > 2.5 mg/dL in the absence of Gilbert's disease	Initiate NUC treatment and monitor weekly or more frequently if clinically indicated until return to baseline levels or within normal reference range. Liver biopsy may be considered if appropriate for participant management.

 
Elevated INR > 0.5 above nadir AND > ULN
 
	
• Abnormal serum albumin > 1 g/dL decrease from baseline	
Confirmed, HBV DNA > 20,000 IU/mL (HBeAg positive) or > 2,000 IU/mL (HBeAg negative) and	Initiating NUC treatment may be considered in discussion with medical monitor.
persistent ALT > ULN without evidence of hepatic toxicity, as defined above, for > 8 weeks	
AIT = alanina aminotransferasa: DNA = dec	vyribonuolaio acid: HRV = hanatitis D virus:

ALT = alanine aminotransferase; DNA = deoxyribonucleic acid; HBV = hepatitis B virus; INR = international normalized ratio; NUC = nucleos(t)ide(s); ULN = upper limit of normal

### **Individual Treatment Modification Criteria**

Study treatment(s) that are considered related by the investigator to any of the following event(s) will be held in a participant until resolution of the event:

- Any study drug-related adverse event  $(AE) \ge Grade 3$
- A confirmed, clinically significant laboratory test abnormality (other than ALT) ≥ Grade 3 considered study drug(s) related by the investigator.

Study treatment(s) may be reinitiated following resolution of the above event(s) after discussion with the medical monitor. Study treatment(s) should be restarted in line with their preassigned schedules.

**Individual Treatment Discontinuation Criteria** 

	Study treatment(s) that are considered related by the investigator to any of the below events will be permanently discontinued:
	
 
Any on treatment uveitis confirmed by ophthalmologic evaluation
 

	• Any confirmed recurrence of study drug—related Grade 3 or 4 (excluding laboratory abnormalities) AE following dose interruption mandates permanent discontinuation of study drug(s)
	
 
Any study drug-related ≥ Grade 3 AE not able to be medically managed (eg, nausea with antiemetics)
 

	
 
Any study drug-related Grade 4 AE (excluding laboratory abnormalities)
 

	• Unacceptable toxicity or toxicity that, in the judgment of the investigator, compromises the ability to continue study specific procedures or is considered not to be in the participant's best interest
	• Any confirmed study drug—related laboratory abnormality ≥ Grade 3 following rechallenge
	A clinically significant Grade 4 laboratory abnormality
	
 
Virological breakthrough as defined in Section 2
 

	Additional criteria for permanent discontinuation of study treatment(s):
	• Intercurrent illness that would, in the judgment of the investigator, affect assessments of clinical status to a significant degree
	
 
Hepatic disease progression or lack of efficacy defined as participants in Cohorts 1 or 2 (Group A), who do not achieve HBsAg decline ≥ 0.2 log10 IU/mL at Week 12
 

	Participant requests to discontinue for any reason
	Participant noncompliance
	Pregnancy during the study
	• At the discretion of the investigator, Gilead, a regulatory agency or an institutional review board (IRB) or independent ethics committee (IEC)
Number of Participants Planned:	Approximately 100 participants

Target Population:	Adult, noncirrhotic, participants with CHB infection who are viremic or virally suppressed on a commercially approved HBV NUC treatment.
Duration of Treatment:	TAF 25-mg tablet will be administered orally once daily for up to 84 weeks, as applicable, in Cohort 1
	VIR-2218 200 mg SC will be administered once every 4 weeks for 24 weeks (6 doses)
	Nivolumab 0.3 mg/kg IV was administered once every 4 weeks for up to 24 weeks (up to 6 doses)
	SLGN 3 mg ( $2 \times 1.5$ -mg tablets) will be administered orally while fasting once a week on the same day for up to 24 weeks (up to 24 doses)
	NOTE: Nivolumab dosing was stopped in this study. This was a sponor decision based on a benefit risk assessment on the use of nivolumab in HBV cure. SLGN was discontinued for Cohort 2 Group B.
Diagnosis and Main Eligibility Criteria:	Male and nonpregnant female participants, ages 18 to 65 years, inclusive, with chronic HBV infection without the presence of cirrhosis, and who are viremic or virally suppressed on NUC treatment for at least 6 months may be eligible for the study.
	Refer to Section 4 of the protocol for detailed Inclusion and Exclusion criteria.
Study Procedures/ Frequency:	This study includes prescreening (optional), screening, treatment, and follow-up assessments.
	After consent is obtained, screening assessments will be completed within 45 days prior to the Baseline/Day 1 treatment. All participants will complete the study treatments described below.
	Cohort 1:
	Screening Visit
	• Treatment Period Visits: Baseline/Day 1, Weeks 4, 8, 12, 13, 14, 16, 20, 24, 28, 32, and 36
	• FU Visits: Weeks 1, 4, 8, 12, 16 (for women of childbearing potential), 24 (Primary), 36, and 48
	Cohort 2:
	Screening Visit
	Group A:
	— Treatment Period Visits: Baseline/Day 1, Weeks 4, 8, 12, 13, 14, 16, 20, 24, 28, 32, and 36

- FU Visits: Weeks 1, 4, 8, 12, 16 (for women of childbearing potential), 24 (Primary), 36, and 48
- Group B:
  - Treatment Period Visits: Baseline/Day 1, Weeks 1, 2, 4, 8, 12, , 14, 16, 20, and 24
  - FU Visits: Weeks 1, 4, 8, 12, 16 (for women of childbearing potential), 24 (Primary), 36, and 48

[figure not shown]
